5.5.5 Online Advertisements

We will recruit participants for treatment studies using a range of postings and online advertising strategies, including but not limited to Facebook, Instagram, Reddit, Craigslist, iConnect, etc. Online advertisements will use IRB approved messages. Interested potential participants will be able to express their interest through calling/emailing study team, or by filling out the IRB-approved REDCap screening survey. Since this REDCap screening survey features open-ended questions, there will not be an automated process enabled to inform these individuals of their eligibility; moreover, eligibility will be determined by study staff reviewing the information entered

into the form, and a prompt will not be used to inform potential patients they are not eligible. Eligible subjects will be contacted at the patient's preferred method of contact, as answered on the survey. For those who are deemed ineligible, the information entered into this REDCap survey will be discarded.

5.6 Duration of Study Participation

After informed consent, participants will complete a single screening session that will take approximately 2 hours. At the next visit, subjects will have a structural MRI performed which take approximately 20 minutes. They will then participate in two PLIFUS/sham sessions over 7 days that include structural and functional MRI scans as well as symptom rating scales and safety assessments. These symptom rating scales and safety assessments will be repeated 1 day after PLIFUS/sham and 7 days after the last PLIFUS/Sham session. We expect this process will take a minimum of 14 days and a maximum of 21 days to complete with a minimum of 3 in-person visits (if consenting, screening and MRI are performed at one visit and the final assessment is performed remotely) and a maximum of 5 in-person visits.

5.7 Total Number of Participants and Sites

The study will be performed at a single site (NYU Langone Manhattan) and participants will be enrolled in order to achieve 12 completers who complete both sonication/sham sessions. Potentially, 4 additional participants will be enrolled if a single session of PLIFUS does not reduce functional connectivity or symptoms in the first 12 completers with good quality imaging data compared to sham, to assess whether 3 sessions of PLIFUS administered over 5 days reduces functional connectivity and symptoms.

Screening and follow-up assessments can be performed at the Psychiatry Research Center at [name] or NYUGSoM Research Imaging Center at [name] MRIs and sonication/sham will always be performed at the NYUGSoM Research Imaging Center at [name] Participants will be recruited at NYU Langone Manhattan, NYU Langone Brooklyn, and Bellevue Hospital.

5.8 Participant Withdrawal or Termination

5.8.1 Reasons for Withdrawal or Termination

Participants are free to withdraw from participation in the study at any time upon request. An investigator may terminate participation in the study if:

- Any clinical Adverse Event (AE), or other medical condition or situation occurs such that continued participation in the study would not be in the best interest of the participant
- The participant meets an exclusion criterion (either newly developed or not previously recognized) that precludes further study participation

5.8.2 Handling of Participant Withdrawals or Termination

If participants withdraw or are terminated before completion of the study, we will attempt to conduct the safety assessments at 24-48 hours and 7 days if the participant experienced one session.

5.9 Premature Termination or Suspension of Study

This study may be temporarily suspended or prematurely terminated if there is sufficient reasonable cause. If the study is prematurely terminated or suspended, the PI will promptly inform the IRB and will provide the reason(s) for the termination or suspension.

Circumstances that may warrant termination or suspension include, but are not limited to:

- Determination of unexpected, significant, or unacceptable risk to participants

The study may resume once concerns about safety, protocol compliance, data quality are addressed and satisfy the IRB and DSMB.

6 Study Agent (Study drug, device, biologic, vaccine etc.) and/or Procedural Intervention

6.1 Study Agent(s) and Control Description

We believe the study will not require an FDA IDE because the PLIFUS parameters are within the FDA ETC safety standards for ultrasound devices. In addition, the PLIFUS sequence targeting globus pallidus used in this protocol has been previously utilized in human subjects without any adverse effects. However, if the IRB requests, we will contact the FDA about the IDE status of this study.

*PLEASE SEE "non-significant risk device assessment" document for detailed reasoning.

6.1.1 Acquisition

PLIFUS delivery into the brain will be verified via an acoustic receiver sensor strapped to the left side of the participant's head. Although the ultrasound energy is concentrated and focused on the GPi, an acoustic emission wave of almost negligible acoustic intensity can be detected from a receiver (ultrasound microphone) strapped to the opposite of the head. This faint signal will be used to confirm the transducer is transmitting into the head. The device operator can observe this signal with an oscilloscope contained in the control system console and it can be observed throughout the duration of the 10 minute sonication period. Sham sonication will not enable the detection of the acoustic emission wave, as there will be no ultrasound transmission into the head during sham.

6.1.2 Formulation, Appearance, Packaging, and Labeling

See the DEVICE MANUAL for device Appearance, Packing, and Labeling details.

6.1.3 Product Storage and Stability

The device platform and all its components are housed in a protective and portable concert instrument box with wheels. Contents can be locked in the box for security and storage.

6.1.4 Preparation

See DEVICE MANUAL for detailed device preparation and calibration procedures.

6.1.5 Dosing and Administration

Pulsed low-intensity focused ultrasound will be delivered over a total of 10 minutes using the following parameters: Pulse repetition frequency: 100 Hz, Pulse Width: 0.5 ms, Duty Cycle: 5%, Sonication Duration: 30s, Inter-Sonation Interval: 30 s. Total Time: 10 minutes. $Ispta = 1.5 \text{ W/cm}^2$ (after passing through skull with estimated 50 % skull attenuation for all subjects). The sham condition will involve the device producing an identical sound as when the FUS is actively penetrating through the skull while an acoustic block is set in front of the transducer, situated under the water membrane. The team administering PLIFUS will consist of a technical expert ([name], or other trained study team member), a research assistant and study psychiatrist. The research assistant, study psychiatrist and participant will be kept blind to treatment assignment (sham or sonication). The PLIFUS/sham administrator will be unblinded to treatment assignments.

6.1.6 Route of Administration

Transcranial guided by neuronavigation.

6.1.7 Starting Dose and Dose Escalation Schedule

The starting dose will be a single session following the parameter specified above (see Dosing and Administration). If an effect on functional connectivity or symptoms is not detected in the first 12 completers, the dose will be changed to three administrations spaced over 5 days using the same sonication parameters for 4 additional participants.

6.1.8 Dose Adjustments/Modifications/Delays

If change in GPi functional connectivity or change in symptoms is not greater following PLIFUS compared to sham with an effect size of at least 0.5 in the first 12 completers, the number of sessions (PLIFUS and sham) will be increased from 1 to 3 for 4 additional participants.

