Statistical Analysis	Because this is a pilot feasibility study, we will examine results after the first 12 participants with good quality imaging data who have completed both phases, and will either continue the study unchanged or, if no signal is detected by fMRI or symptom change, we will switch to administering 3 sessions of PLIFUS or sham over 5 days. We will define our threshold for signal detection as an effect size of 0.5 or greater for the comparison between treatment groups (PLIFUS or sham) of change of biomarkers (fMRI and symptom severity) from baseline to post-treatment. All results will be considered exploratory. Formal statistical analyses will be performed using standard methods for a random-over crossover design; safety outcomes will be descriptive.

Schematic of Study Design

1 Key Roles

[name]

Department of Psychiatry, NYU Langone Medical Center
[name]
[name]
[contact]
[contact]

[name] (Co-PI)

Department of Psychiatry, NYU Langone Medical Center
[name]
[name]
[contact]
[contact]

[name]

Department of Psychiatry, NYU Langone Medical Center
[name]
[name]
[contact]
[contact]

[name], Statistician

Department of Population Health, NYU Langone Health
[name]
[name]
[contact]
[contact]

F. [name]

Department of Child and Adolescent Psychiatry, NYU Langone Medical Center
[name]
[name]
[contact]
[contact]

2 Introduction, Background Information and Scientific Rationale

2.1 *Background Information and Relevant Literature*

2.1.1 **The Need for New Treatment Approaches in Schizophrenia**

Schizophrenia is a disabling chronic illness characterized by psychosis (delusions and hallucinations), negative symptoms (apathy and reduced emotional expression) and cognitive deficits. Antipsychotic medications, which block dopamine transmission, substantially improves delusions and hallucinations in approximately 60% of patients, but side effects are poorly tolerated and relapse is common ¹. Psychosis can be very distressing for patients and their families, often results in hospitalization, and may contribute to violence. Currently there is no effective treatment for negative symptoms and cognitive deficits.

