We will use the ultrasound pulse parameters used by Cain et al ³⁹ for sonication of the globus pallidus (see previous paragraph) because their experiment demonstrated hemodynamic effects without adverse effects in healthy subjects and the stimulation parameters were very low-intensity and extremely low risk. If we do not see effects on functional connectivity or symptoms after the first 5 participants and if the single sessions are well-tolerated, we will switch to repeated dosing, applying three PLIFUS or sham sonifications over 5 days since repeated exposures may be required to produce detectable effects. A single session of PLIUS will include 5 minutes net total dosage of PLIFUS. The exposure uses ten 30 sec blocks of PLIFUS sonication with 30 sec rests in-between spread over ten minutes. Sonication will be delivered (Fig. 3) in low-amplitude pulses using a carrier wave frequency: 361 kHz, pulse repetition frequency: 100 Hz, and duty cycle: 5 % yielding an I_{spta} 1.5 W/cm² at the Gpi. The acoustic intensity used is in the range of FDA and Electrotechnical Technical Commission (ETC) regulation standards for diagnostic and therapeutic ultrasound, respectively ²⁸.

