7.2.4 Intervention Visits

Intervention Visit 1: (Day 0)

- Administer CGI, C-SSRS, SAFTEE, SAFTEE addendum, and PSYRATS
- Obtain structural MRI scan for fMRI registration (5 minutes)
- Obtain fMRI resting state scan (20 minutes)
- Administer AHRS and DESA prior to starting intervention
- Administer PLIFUS/sham over 10 minutes (re-administer AHRS and DESA at 5 minutes)
- Repeat AHRS and DESA immediately after PLIFUS/sham
- Obtain structural MRI scan for fMRI registration (5 minutes)
- Obtain fMRI resting state scan (20 minutes)
- AHRS and DESA repeated immediately after fMRI scan
- PSYRATS and CGI 60 minutes after PLIFUS/sham
- Psychiatric and medical assessment, including MoCA, SAFTEE, and SAFTEE addendum, 1 hour after PLIFUS/sham

Intervention Visit 1B: (Day 1-2) (may be remote)*

- AHRS and DESA
- SAFTEE & addendum
- C-SSRS

Intervention Visit 2 (Day 6-8)

- Administer CGI, C-SSRS, SAFTEE, SAFTEE addendum, and PSYRATS
- Obtain structural MRI scan for fMRI registration (5 minutes)
- Obtain fMRI resting state scan (20 minutes)
- Administer AHRS and DESA prior to starting intervention
- Administer PLIFUS/sham over 10 minutes (re-administer AHRS and DESA at 5 minutes)
- Repeat AHRS and DESA immediately after PLIFUS/sham
- Obtain structural MRI scan for fMRI registration (5 minutes)
- Obtain fMRI resting state scan (20 minutes)
- AHRS and DESA repeated immediately after fMRI scan
- PSYRATS and CGI 60 minutes after PLIFUS/sham
- Psychiatric and medical assessment, including MoCA, SAFTEE, and SAFTEE addendum, 1 hour after PLIFUS/sham

Intervention Visit 2B (Day 7-9) (may be remote)*:

- AHRS and DESA
- SAFTEE & addendum
- C-SSRS

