addition to all adverse events recorded by the SAFTEE assessments, the DSMB will receive a report of any additional participant complaints, instances of participant distress, or breaches of confidentiality. Because this is a pilot study with a very small sample size, formal statistical criteria are not identified in advance for a stopping rule. The DSMB may halt the study for reasons of safety—we are not aware of any significant safety concerns. The DSMB must approve the decision to switch from one session of PLIFUS to 3 sessions if no effect is detected after the first 12 completers with good quality imaging data. A failure to detect an effect size of 0.5 or greater compared to sham on the AHRS, DESA, and PSYRATS total score or on GPi functional connectivity after the first 12 participants will define “no effect” and trigger a switch to 3 treatment sessions over 5 days for phase II of the study which will involve an additional 4 participants. The DSMB will also be provided copies of all communications with the IRB. The DSMB will meet prior to initiation of the study and a minimum of every six months and will be provided data regarding enrollment and side effects and a study summary prior to each meeting. [name] and study staff will not attend the closed section of the DSMB meetings. Throughout the study, notification of any Serious Adverse Events (SAEs) as well as any proposed investigator-initiated changes in the protocol will be submitted to the DSMB. Based on its review of the revised protocol, the DSMB will identify the data parameters and format of the information to be regularly reported. All SAEs and adverse events will be tabulated and submitted to the IRB and DSMB in the bi-annual (every 6 months) data reports or at the time of continuing review. AEs will be reported to the IRB annually (at continuing review) if they are expected, related, and harmful. A summary of the outcomes of the safety reviews as prepared for the DSMB along with accumulated adverse events and deviations will be submitted to the IRB as part of an annual progress report at the time of the Continuing Review submission.

8 Clinical Monitoring

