A study psychiatrist will be present during all sessions of PLIFUS and sham. Participants will be monitored during and after sonication until psychiatrically cleared by the study psychiatrist 1 hour after completion of each session. Participants will be contacted 24-48 hours and 7 days after each treatment period and symptoms, side effects and suicidality assessed.

9 Statistical Considerations

This is a pilot study intended to obtain preliminary data to guide future studies. The analysis will primarily be descriptive for this purpose and, due to the small sample size, effect sizes will be the primary signal of target engagement. Consistent with other studies in the field, we have selected an effect size of 0.5 as our threshold. In addition, there is a pre-planned review of results after completion of the first 5 participants; the administration of PLIFUS/sham will be increased from one session to three sessions over 5 days if an effect size of 0.5 or greater with PLIFUS is not detected in change from baseline in GPi functional connectivity or symptom response compared to sham.

The primary statistical analysis will be performed in completers without imputation of missing data and will be change in primary outcomes (GPi functional connectivity and symptom severity) from baseline to the first measure post-sonication or sham (immediately post-sonication for symptoms; 10-30 minutes for fMRI). PLIFUS and sham PLIFUS will be compared using a linear mixed effects model with baseline measures (GPI functional connectivity and severity of psychotic symptoms) as continuous variables; treatment (PLIFUS or sham) and sequence as categorical variables; and participant as a random effect. Similar secondary exploratory analyses will be performed at additional time points (symptom severity during sonication, 60 minutes, 1 day and 7 days after sonication). Secondary analyses of other outcome measures (BPRS total score, PSYRATS and CGI) will be analyzed following the same approach. Safety measures, including the SAFTEE and C-SSRS will be summarized descriptively. If the study design is adapted (sonication increased to 3 sessions) after the first 12 completers with good quality imaging data, results from the first 12 completers and subsequent 4 participants will be analyzed separately.

Sample Size

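### Section 6.1.8 as written moves to three sessions if either connectivity or symptoms misses 0.5, while the rest of the protocol does so only if neither responds; two sections still place the switch after 5 participants

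*Combined protocol and SAP*

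**What the plan says.** The dose-modification rule in 6.1.8 begins "If change in GPi functional connectivity or change in symptoms is not greater following PLIFUS compared to sham with an effect size" and sets the threshold at 0.5 or more in the first 12 completers. If the condition is met, sessions go from 1 to 3 for 4 further participants.

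The section directly before it, 6.1.7, states the same switch differently: "If an effect on functional connectivity or symptoms is not detected in the first 12 completers". The Statistical Analysis row of the Protocol Summary has "if no signal is detected by fMRI or symptom change, we will switch to administering 3 sessions of PLIFUS or sham over 5 days", next to the same 0.5 threshold. Objective 5 and the Population and Number of participants rows of the Summary, and Sections 4.1 and 5.7, follow the same pattern at 12 completers.

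Two sections use that pattern with a different sample. Section 2.1.4 reads "If we do not see effects on functional connectivity or symptoms after the first 5 participants". Section 9 places its planned review after 5 participants and switches "if an effect size of 0.5 or greater with PLIFUS is not detected in change from baseline in GPi functional connectivity or symptom response". Later in Section 9, the adaptation is described as coming after 12 completers.

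Section 7.15 defines the absence of an effect for the DSMB. Its sentence starts "A failure to detect an effect size of 0.5 or greater compared to sham on the AHRS, DESA, and PSYRATS total score or on GPi", goes on to name connectivity, and sets the review after 12 participants. It does not say how many of the three scales must reach 0.5.

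**The concern.** Section 6.1.8 is where a reader would look for the operative rule. Its wording says that the change in A or the change in B is not large enough, which is satisfied when one of the two falls short. The other sections deny an effect on A or B, which is satisfied only when both fall short. For any result with one domain above 0.5 and one below, the two rules give opposite instructions.

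The primary endpoint is connectivity. A trial with a 0.6 effect on connectivity and little symptom change would be a detected signal under 6.1.7 and a failure under 6.1.8. In the second case, 4 more people with active psychosis would be asked to have three PLIFUS and three sham sessions.

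The leftover review at 5 participants is a second conflict in the same rule. The unspecified number of scales in 7.15 is a third. Section 5.1 admits participants on a single psychosis item, so someone with delusions only has little room to improve on AHRS, and the choice between any and all scales can decide the outcome.

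**Working it through.** **Wording, side by side**

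| Place | Condition for three sessions | Sample |
|---|---|---|
| 6.1.8 | either domain below 0.5 (literal) | 12 |
| Summary (Objectives, Population, Number of participants, Statistical Analysis), 4.1, 5.7, 6.1.7 | neither responds | 12 |
| 2.1.4, Section 9 switching rule | neither responds | 5 |
| 7.15 definition | leans to neither; scale count not given | 12 |
| Summary (Brief Summary), 13.8 | fMRI and symptoms not detected; less clear | 12 |

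Section 3, and an earlier sentence in 7.15, speak of no measurable effects, which fits neither. Section 6.1.8 is the outlier.

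**Size.** The protocol gives no switching probability to reproduce and does not define the effect-size denominator. Assumptions that are not in the documents: the effect size is the paired standardised difference dz in the favourable direction, data are normal, symptom scales correlate 0.3-0.7 with each other, and connectivity correlates 0-0.5 with symptoms. From the documents: n = 12 and threshold 0.5.

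Step 1. One measure: P(observed dz ≥ 0.5) = P(noncentral t, 11 df, noncentrality d√12, ≥ 0.5√12 = 1.732). At true d = 0, 0.2, 0.5 and 0.8 this is 0.056, 0.174, 0.515 and 0.844.

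Step 2. Two independent measures with probabilities p1 and p2 of reaching 0.5. Switch if either misses: 1 − p1·p2. Switch only if neither reaches it: (1 − p1)(1 − p2).
- No true effect: 1 − 0.0556² = 0.997 against 0.9444² = 0.892.
- Both true effects 0.5: 1 − 0.5152² = 0.735 against 0.4848² = 0.235.
- Connectivity 0.8, symptoms 0: 1 − 0.8444 × 0.0556 = 0.953 against 0.1556 × 0.9444 = 0.147.

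Step 3. Simulation of connectivity plus three scales over nine correlation settings (60,000 trials each). With a true connectivity effect of 0.5, the share of trials reaching 0.5 on connectivity that 6.1.8 would still switch is:

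| True symptom effect | Any of three scales counts | One named scale |
|---|---|---|
| 0 | 76-89% | 90-95% |
| 0.2 | 44-69% | 73-83% |
| 0.5 | 6-29% | 34-49% |

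Step 4. Scale count under the neither rule:

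| Symptom criterion | False signal, no true effect | No effect called, all true effects 0.5 |
|---|---|---|
| One named scale | 10-11% | 23-32% |
| Any of three | 15-19% | 9-21% |
| All three | 6-7% | 33-45% |

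Step 5. Review at 5 instead of 12, neither rule, two independent measures, no true effect. At n = 5, P(dz ≥ 0.5) = 0.163, so the chance of a false signal is 1 − 0.837² = 0.30. At 12 it is 1 − 0.892 = 0.108.

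**The case against.** The strongest reply is that this is one loosely drafted sentence whose neighbour, 6.1.7, states the intended rule. The DSMB includes a statistician, must approve the switch and decides without statistical tests. It is unlikely to call 0.6 on the primary endpoint no effect. Most of this stands, and it is why the point is minor. It does not make 6.1.8 right: that section carries both the threshold and the action, and it gives the wrong instruction.

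A reader might go further in four ways that the documents do not support.

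- *That 7.15 also adopts the either rule, or leaves the matter open.* Its sentence has the same negated form as 6.1.7 and Section 9, the sentence before it speaks of no effect being detected, and the term defined is no effect. It leans clearly to neither. Only the scale count is missing.
- *That PSYRATS cannot serve in the trigger.* Section 9 sets "immediately post-sonication for symptoms; 10-30 minutes for fMRI", and 7.2.4 has "PSYRATS and CGI 60 minutes after PLIFUS/sham" as the only post-session rating. But Section 9 defines the outcome as change to the first post-session measure and applies the same approach to PSYRATS, which gives 60 minutes. What is left is that 7.15 does not refer to Section 9 and that the parenthesis does not fit PSYRATS.
- *That 90-95% is the size of the problem.* That range needs a literal reading of 6.1.8 and also a single named scale, which the protocol never specifies.
- *That the error affects inference.* Results are exploratory, and the 12 and the 4 are analysed separately.

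The simulation also has no floor effect and no mix of hallucination-only and delusion-only participants, so it does not measure that part of the concern.

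**Conclusion.** The rule in 6.1.8 is wrong as written. It contradicts the Protocol Summary, 4.1, 5.7 and 6.1.7, and it is probably a drafting slip. The trigger after 5 participants in 2.1.4 and in Section 9's switching rule conflicts with the 12-completer rule used elsewhere, including later in Section 9. The any-or-all question in 7.15 is a real but smaller gap.

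If 6.1.8 were followed literally, most trials with a connectivity signal and no symptom effect would be switched. That conclusion rests on the stated assumptions about the effect-size formula, normality and correlations, and on someone applying the sentence mechanically. The practical consequence is confined to whether the four-participant stage opens, subject to DSMB approval. Severity: minor. Confidence in the wording conflict is high; the percentages are illustrative.

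**What to change.** Reword 6.1.8 along these lines, and use the same wording in 7.15:

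*Only if, at the review of the first 12 completers with usable imaging, the effect size for reduction versus sham is below 0.5 for GPi functional connectivity AND below 0.5 for symptoms will three sessions replace one, for 4 further participants.*

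In 2.1.4 and in Section 9's switching rule, replace 5 participants with 12 completers. The safety report to the DSMB after 5 subjects in 7.15 is a separate matter and can stay.

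In 7.15, before the 12-completer review, state whether any or all of AHRS, DESA and PSYRATS must reach 0.5, each at its first post-session measure (PSYRATS at 60 minutes). That choice belongs to the sponsor. Any of three suits a sample in which some people have only hallucinations or only delusions, at a false-signal chance of about 15-19% against 6-7% for all three.

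The cost is wording, with IRB and DSMB approval, and no new data or patients. The DSMB loses some flexibility. The three-session stage also opens less often: with no true effect and one named scale or any of three, it stays closed in about 10-19% of trials, against 0.3-3% under 6.1.8 as written.
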